## 4. INVESTIGATIONAL PLAN

### 4.1. Overall Study Design

[figure not shown]
This is a Phase 2, randomized, double-blind, double-dummy study in subjects with ET who are resistant to or intolerant of HU (according to modified ELN criteria) with a screening platelet count  $\geq 650 \times 10^9/L$  and WBC count  $\geq 11.0 \times 10^9/L$ . Subjects will be randomized in a 1:1 ratio, stratified by JAKV617 mutation status (positive vs negative), platelet count at screening ( $\geq 1000 \times 10^9/L$  or  $< 1000 \times 10^9/L$ ), and prior anagrelide use (yes vs no) to the following 2 treatment groups:

- Group A: ruxolitinib at a dose of 10 mg BID orally and anagrelide-placebo.
- Group B: anagrelide at a dose of 1 mg BID orally and ruxolitinib-placebo.

The study will enroll approximately 120 subjects. Due to block randomization and stratification, the 2 treatment groups may not each contain exactly the targeted number of subjects (n = 60).

Subjects will receive blinded study treatment for 52 weeks. Options for the open-label treatment phase are detailed in Section 4.1.1. All subjects will be followed for safety (eg, reporting of AEs and SAEs) 30 to 37 days after the last dose of blinded study treatment or open-label study treatment. The overall study design is shown in Figure 1.

**Figure 1: Study Design**

#### **4.1.1. Options for the Open-Label Treatment Phase**

Subjects originally randomized to ruxolitinib with anagrelide placebo (Group A) who are receiving benefit from therapy can 1) continue receiving open-label ruxolitinib until the study is concluded or they meet discontinuation criteria, or 2) choose to discontinue therapy.

Subjects originally randomized to receive anagrelide plus ruxolitinib placebo (Group B) have 3 options: 1) they may cross over to begin receiving ruxolitinib if they meet eligibility criteria after consultation with the sponsor and may then continue until the study is concluded or they meet discontinuation criteria; 2) they may continue receiving anagrelide until the study is concluded or they meet discontinuation criteria; or 3) they can choose to discontinue therapy. Note that subjects originally randomized to Group B may cross over to receive ruxolitinib at any time during the open-label part of the study.

Subjects who will continue with the same active agent to which they were randomized will have a study visit at Week 56, at which time study drugs will switch over to open-label supplies (ruxolitinib or anagrelide) and then study visits every 12 weeks (Week 68, 80, etc). Subjects who were originally randomized to anagrelide (Group B) and who cross over to ruxolitinib will begin receiving ruxolitinib at the Week 56 visit. These subjects will have study visits at Weeks 1, 2, 3, 4, and every 4 weeks up to 52 weeks, then every 12 weeks thereafter. Subjects who initially remain on anagrelide after unblinding but choose to cross over to receive ruxolitinib at a later time will have study visits at Weeks 1, 2, 3, 4, and every 4 weeks up to 52 weeks, then every 12 weeks thereafter.

#### **4.2. Measures Taken to Avoid Bias**

This is a randomized, double-blind, placebo-controlled study with a composite primary endpoint, defined as the proportion of subjects who complete at least 52 weeks of treatments and who achieve a simultaneous reduction of platelet count to  $< 600 \times 10^9/L$  and of WBC count to  $< 10 \times 10^9/L$  for at least 80% of biweekly measurements for 12 consecutive weeks between Weeks 32 and 52. Subjects will receive blinded study drug (ruxolitinib + anagrelide placebo or anagrelide + ruxolitinib placebo).

Centralized randomization numbers within each stratum will be created for treatment assignment. Subjects will be stratified by presence/absence of the JAK2 V617F mutation, screening platelet count, and prior anagrelide use. Subjects will be assigned to study treatment in accordance with the randomization schedule. Subjects, investigators, and the study team will be blinded to treatment assignment. A sponsor statistician who is not part of the study team will be unblinded and may provide summary-aggregated data by treatment group to the sponsor and/or the Data Monitoring Committee (DMC), but individual subject data will remain blinded.

#### **4.3. Number of Subjects**

Approximately 120 subjects will be randomized in a 1:1 ratio to 1 of 2 treatment groups (approximately 60 subjects per group).

#### 4.4. Duration of Treatment and Subject Participation

After signing the ICF, subject study participation is estimated to average approximately 24 to 36 months per individual subject:

**Screening** (Day -35 to Day -8): Up to 28 days.

**Baseline (pretreatment) period** (Day -7 to Day -1): 7 days before the first dose of treatment (required for all eligible subjects to complete the daily symptom diary for 7 days before the first dose of study medication).

**Blinded Treatment Phase** (Day 1 through Week 52): Begins with first dose of either ruxolitinib plus anagrelide-placebo or anagrelide plus ruxolitinib-placebo (Day 1). The efficacy assessment period will be defined by collection of blood samples every 2 weeks between Weeks 32 and 52.

**Open-Label Treatment Phase** (Crossover and Extension Period): After each individual subjects reach the Week 52 study visit (and all data through the Week 52 visit have been entered to the eCRF and the data verified), crossover to an open-label extension may occur. Once Week 52 data completion has been confirmed, the study subject and the investigator will be unblinded to study treatment assignment. The subjects will be brought into the study clinic for the unblinding crossover visit, which is designated as Week 56 in the schedules of assessments (Table 3 and Table 5).

Subjects originally randomized to anagrelide (Group B) will be evaluated for eligibility to cross over to open-label ruxolitinib according to investigator's decision and if subjects meet safety criteria (eg, they do not now meet any exclusion criteria that would have precluded their participation in the study), after consultation with the sponsor. Subjects originally randomized to ruxolitinib (Group A) who are receiving benefit from therapy will continue receiving open-label ruxolitinib until the study is concluded. All subjects will be followed for safety (eg, reporting of AEs and SAEs) 30 to 37 days after last dose of blinded study treatment or open-label study treatment.

**Follow-up period:** 30 to 37 days after the last dose of blinded study treatment or open-label ruxolitinib.

#### 4.5. Overall Study Duration

The study begins when the first subject signs the ICF. The blinded treatment phase is complete and study data analysis can occur for the primary endpoint when all subjects have completed Week 52 or discontinued, and all study data through the Week 52 visit have been entered and the data cleaned and verified. The database will be frozen at this time for the initial data analysis to occur.

The study is completed when the last subject has reached Week 156 (approximately 3 years of treatment). Individual subject participation is expected to average 24 to 36 months.

#### 4.6. Study Termination

The investigator retains the right to terminate study participation at any time, according to the terms specified in the study contract. The investigator is to notify the institutional review board

(IRB)/independent ethics committee (IEC) in writing of the study's completion or early termination, send a copy of the notification to the sponsor or sponsor's designee, and retain 1 copy for the site study regulatory file.

The sponsor may terminate the study electively, if required by regulatory decision, or upon advice of the DMC. If the study is terminated prematurely, then the sponsor will notify the investigators, the IRBs and IECs, and regulatory bodies of the decision and reason for termination of the study.

## **5. TREATMENT**

### **5.1. Treatment Assignment**

#### **5.1.1. Subject Numbering and Treatment Assignment**

Each subject will be identified in the study by a subject ID number, which is a combination of the site ID and subject number (see Section 7.2).

Enrollment will be controlled by an interactive voice/web response system (IXRS).

Study sites will enter subject demographic and baseline data into the IXRS in order to receive a subject number and treatment allocation.

All subject numbers will be 6 digits; the first 3 digits will be the site number, and the last 3 digits will be the subject's number. This subject number will be maintained throughout the study and will not be reassigned. Subjects who withdraw consent or discontinue from the study after being assigned a subject number will retain their initial number.

Site staff will contact the IXRS to allocate the subject to treatment assignment and obtain the initial study drug assignment. The investigator or designee will select the assigned units of study drug from their stock that correspond to the number provided by the IXRS and dispense the study drug to the subject. All subsequent dispensing of study drug should follow this process. Refer to the IXRS manual for detailed information.

If a subject is mistakenly given a bottle of study drug that is not the bottle assigned by the IXRS, then the IXRS help desk must be notified immediately. The reason for the misallocation of the study drug must be documented by the study site and reported to the IRB/IEC.

For subjects who signed an ICF but are not allocated and for subjects who are allocated but were not treated, refer to the electronic case report form (eCRF) Completion Guidelines for instruction on which eCRFs to complete.

#### **5.1.2. Randomization and Blinding**

Subjects will be randomly assigned to either Group A or Group B through central randomization by the IXRS. Full details will be provided in the IXRS manual.

Subjects, investigators, and the sponsor will remain blinded to each subject's treatment assignment throughout the study. Emergency unblinding will occur if an AE requires the investigator to be made aware of the subject's treatment assignment.

### **5.1.2.1. Blinding and Unblinding**

Treatment assignment should remain blinded to the investigators, subjects, and sponsor as long as the blinded treatment period continues for that subject. Unblinding of treatment assignment may occur in 2 different circumstances: emergency unblinding and scheduled unblinding for individual subjects after Week 52.

#### **5.1.2.1.1. Emergency Unblinding**

The investigator will, whenever possible, discuss options with the sponsor's medical monitor before initiating the emergency unblinding procedure. If the investigator is unable to contact the sponsor before unblinding, then the investigator must notify the sponsor as soon as possible after the unblinding incident. In addition, the investigator will record the date and reason for revealing the blinded treatment assignment for that subject. Refer to the IXRS manual for detailed emergency unblinding procedures.

If an SAE (as defined in Section 8.3) is reported to the sponsor, then the sponsor may choose to unblind the treatment assignment for the individual subject. If an expedited regulatory report to 1 or more regulatory agencies is required, then the report will identify the subject's treatment assignment. When applicable, a copy of the regulatory report may be sent to investigators in accordance with relevant regulations, the sponsor's policy, or both.

Generally, emergency unblinding will occur only in the case of a serious medical event for which knowledge of the treatment assignment is critical for the acute medical management of the subject's condition. Subjects experiencing this type of event will be withdrawn from study participation for safety reasons.

#### **5.1.2.1.2. Scheduled Unblinding**

After each individual subject completes the Week 52 visit, and when all data for each subject have been entered into the eCRFs and cleaned and verified, unblinding for an individual subject can occur. Subjects will be brought to the study clinic for the unblinding/crossover visit, which is designated Week 56 in the schedules of assessments (Table 3 and Table 5). Subjects who will continue receiving the study drug to which they were originally randomized will have subsequent visits every 12 weeks (Week 68, 80, etc).

Subjects who are unblinded and cross over to start ruxolitinib for the first time will have study visits at Weeks 1, 2, 3, 4, and every 4 weeks up to 52 weeks, then every 12 weeks thereafter.

The unblinding of study treatment before Week 52 will only occur for medical emergency purposes (SAE for which unblinding is necessary for medical management) and will result in withdrawal from the study.

## **5.2. Study Drug**

### **5.2.1. Ruxolitinib**

#### **5.2.1.1. Description and Administration**

Ruxolitinib or matching placebo will be provided as 5 mg tablets packaged in high-density polyethylene (HDPE) bottles. Ruxolitinib or matching placebo will be self-administered as a BID oral treatment.

Doses of ruxolitinib or matching placebo should be self-administered with approximately 12 hours apart without regards to food.

Note that subjects must be instructed to withhold the morning dose of ruxolitinib or matching placebo until reaching the clinic for each study visit where dose administration will occur. The dose must be reduced or interrupted for declining platelet count, hemoglobin, or ANC as described in Section 5.4 and will be increased or restarted with recovery of hematologic parameters.

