## 5.4. Treatment Modifications: Increases, Interruptions, and Adjustments

Subjects randomized to either study group will be receiving both an active drug and a placebo (dummy drug). Neither the investigator nor the subject will know which is the active drug and which is the placebo. Thus, in order to maintain the blind, when dose modification is required, both of the study drugs will be titrated together.

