### 5.4.1. Dose Increases for Inadequate Efficacy

Dose increases will be permitted for inadequate efficacy. Dose increases for subjects meeting prespecified criteria for inadequate efficacy will be permitted after 2 weeks of therapy, and dose decreases for safety are allowed at any time. Doses of both study drugs will be titrated simultaneously using different dose levels as shown in [Table 2](#). Anagrelide or anagrelide placebo and ruxolitinib or ruxolitinib placebo increases are permitted per investigator discretion and taking into account the manufacturer's instructions, labeling, and subject's medical condition.

Each dose escalation must be at least 1 week apart, and subjects must meet all of the following criteria:

1. Platelet count  $\geq 150 \times 10^9/L$
2. Hemoglobin  $\geq 9$  g/dL.
3. ANC  $\geq 1500 \times 10^9/L$ .
4. One or more of the following:
  - a. Platelet count  $> 600 \times 10^9/L$ .
  - b. WBC count  $> 10 \times 10^9/L$ .
  - c. Minimal improvement, no change, or worsening of vasomotor symptoms including headache, lightheadedness, syncope, atypical chest pain, acral paresthesia, livedo reticularis, erythromelalgia, and transient visual disturbances (eg, amaurosis fugax, scintillating scotomata, ophthalmic migraine).

Additionally, it is recommended that safety hematology be performed within 14 days of a dose increase to confirm that a safe dose has not been exceeded. Doses may be increased by 5 mg BID for ruxolitinib or ruxolitinib-placebo. These are per investigator discretion and taking into account the manufacturer's instructions, labeling, and subject's medical condition. The dose of ruxolitinib or ruxolitinib-placebo will never exceed 25 mg BID.

Doses of anagrelide or anagrelide placebo may not be increased by more than 0.5 mg/day per week from the previous dose or to a dose that was not previously tolerated by the subject. The dose of anagrelide or anagrelide placebo should not exceed 2.5 mg BID (and 2.5 mg in a single dose). The maximum dose of anagrelide is 2.5 mg BID (5 mg total per day), which corresponds to a high maintenance dose used in practice.

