**Table 1: Dose Interruptions for Hematologic Toxicities**

Parameter	Dose Reduction by 1 Dose Level If:	Hold If	Reinstitute Drug at 1 Dose Level Lower When Recovered to
Hematocrit (%)	< 35%	< 30%	≥ 35%
ANC ( $\times 10^9/L$ )	< $1.5 \times 10^9/L$	< $1.0 \times 10^9/L$	≥ $1.25 \times 10^9/L$
Platelet count ( $\times 10^9/L$ )	< $150 \times 10^9/L$	< $100 \times 10^9/L$	≥ $125 \times 10^9/L$

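### Protocol Section 5.2 promises a dose increase on blood-count recovery that Section 5.4 does not provide, and the stated 5 mg BID ruxolitinib step is wrong below the starting dose

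*Protocol*

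**What the plan says.** **On recovery of counts.** Section 5.2.1.1 (ruxolitinib) and Section 5.2.2.1 (anagrelide) refer to Section 5.4 for reductions and interruptions, then add that the dose "will be increased or restarted with recovery of hematologic parameters". In Section 5.4, the recovery column of Table 1 is headed "Reinstitute Drug at 1 Dose Level Lower When Recovered to". The increase rule is in 5.4.1: "Dose increases will be permitted for inadequate efficacy", at the investigator's discretion. It adds that "Each dose escalation must be at least 1 week apart, and subjects must meet all of the following criteria". Those criteria are floors for platelets, hemoglobin and ANC, plus at least one of platelets above 600 × 10^9/L, WBC above 10 × 10^9/L, or vasomotor symptoms that have not clearly improved. Section 6.3 sends dose adjustment for hematologic safety to Section 5.4.

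**On the size of an increase.** Section 5.4.1 states "Doses may be increased by 5 mg BID for ruxolitinib or ruxolitinib-placebo", and the synopsis gives the same step. Section 5.4.1 also says "Doses of both study drugs will be titrated simultaneously using different dose levels as shown in" Table 2, and that "Doses of anagrelide or anagrelide placebo may not be increased by more than 0.5 mg/day per week from the previous dose". Section 5.4 explains the pairing: "in order to maintain the blind, when dose modification is required, both of the study drugs will be titrated together". Section 5.4.4 carries the same rules into the open-label phase, with Table 2 read for each drug on its own.

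**The concern.** These are live dosing instructions for subjects whose dose has already been lowered for toxicity. If Section 5.2 is followed, a recovered subject's dose goes up; if Section 5.4.1 is followed, it may have to stay where it is. Two sites could treat the same subject differently.

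The step size raises a second question. If 5 mg BID is applied below the starting dose, the increase is twice the spacing of Table 2, and from one level it goes past the starting dose altogether.

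The affected levels are easy to reach. Subjects start at DL 1, so a first one-level reduction from there lands on DL -1. Table 1 requires a reduction at hematocrit below 35%. Section 1.5.1 names anemia as the most frequent treatment-emergent event in the sponsor's earlier ET study. The inclusion criteria set no minimum hemoglobin or hematocrit.

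**Working it through.** **Part 1: the recovery rule.** Set Section 5.2 against every rule in Section 5.4 that raises or restores a dose.

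- Table 1: restart after a hold, one level lower. This supports the restart half of the Section 5.2 sentence.
- 5.4.1: increase for inadequate efficacy, with all criteria met. Recovery of counts is not a trigger.
- 5.4.2.3: return to the previous BID regimen after a CYP3A4 or CYP1A2 inhibitor course ends. This is not hematologic recovery.

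Nothing supports the increase half. As an illustration, take a subject reduced without a hold whose counts recover to platelets 500 and WBC 9 (× 10^9/L), with improved symptoms. Section 5.2 says the dose goes up. None of the three alternatives in criterion 4 of 5.4.1 is met, so 5.4.1 does not allow it.

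**Part 2: the step size.** Inputs are the morning and evening doses in Table 2. Daily dose = AM + PM. One-level step = daily dose at the next level − daily dose at the current level. Stated step = +5 mg AM and +5 mg PM = +10 mg/day.

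The plan's figure first. From the start upward the one-level steps are 30 − 20, 40 − 30 and 50 − 40, each 10 mg/day, so 5 mg BID is reproduced in 3 of 3. Below the start they are 10 − 5, 15 − 10 and 20 − 15, each 5 mg/day, so it is reproduced in 0 of 3.

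| From | Ruxolitinib now, AM/PM (mg/day) | One Table 2 level up | Adding 5 mg BID | Where that lands |
|---|---|---|---|---|
| DL -3 | 5/0 (5) | 5/5 (10), +100% | 10/5 (15), +200% | DL -1, skipping DL -2 |
| DL -2 | 5/5 (10) | 10/5 (15), +50% | 10/10 (20), +100% | DL 1, skipping DL -1 |
| DL -1 | 10/5 (15) | 10/10 (20), +33% | 15/10 (25), +67% | no row |
| DL 1 | 10/10 (20) | 15/15 (30) | 15/15 (30) | DL 2 |
| DL 2 | 15/15 (30) | 20/20 (40) | 20/20 (40) | DL 3 |
| DL 3 | 20/20 (40) | 25/25 (50) | 25/25 (50) | DL 4 |

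The DL -1 result is 25/20 = 125% of the starting daily dose, and it has no paired anagrelide dose.

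**Paired anagrelide.** Daily doses are 0.5 (DL -3), 1.0 (DL -2), 1.5 (DL -1) and 2.0 mg (DL 1).

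- DL -3 to DL -1: 1.5 − 0.5 = +1.0 mg/day.
- DL -2 to DL 1: 2.0 − 1.0 = +1.0 mg/day.
- Cap: 0.5 mg/day per week, so each skip is 1.0/0.5 = 2 times the cap.
- One-level moves: 0.5 to 1.0 to 1.5 to 2.0, each +0.5 mg/day, exactly at the cap.

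From DL 1 upward, Table 2 spreads each 1.0 mg/day rise over two weekly rows. Below DL 1 the Week 1 and Week 2 rows are identical, so it offers no such split for a two-level move.

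**Open-label phase.** On ruxolitinib alone the anagrelide cap has nothing to act on. A step from DL -2 to 20 mg/day, or from DL -3 to 15 mg/day, lands on a listed level and is not limited by it.

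**A related slip.** The synopsis and 5.4.1 print the ANC floor for escalation as 1500 × 10^9/L. Table 1 uses 1.5 × 10^9/L for the reduction limit; 1500/1.5 = 1000. Read literally, the criterion cannot be met.

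**The case against.** The strongest reply is that the wording is permissive. The 5 mg BID increase is allowed, not required, and 5.4.1 says first that titration follows Table 2. Nothing forbids a smaller step, and a one-level move keeps the pairing and meets the cap. This stands. A reader might infer that 5 mg BID, the paired levels and the weekly cap cannot all be respected, leaving no permitted move while blinded. The documents do not support that, because it requires reading a permission as an exact, compulsory step.

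Other parts of the reply also stand:

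- Section 5.2 is descriptive, and Section 6.3 points to Section 5.4, so 5.4 is very probably meant to govern.
- A site that follows Table 2 cannot arrive at 15/10 mg in either phase.
- The open-label skips end at or below the starting dose; their large percentages reflect small starting amounts.
- Every 5.4.1 increase still needs the count floors and at least a week's spacing, and a blood count within 14 days is recommended.
- Section 5.4.1 also bars raising anagrelide or its placebo to a dose the subject has not tolerated before. While the drugs move together, that limits re-escalation of both.

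What the reply does not remove is that Section 5.2 makes an unconditional statement with no rule behind it, and that neither the synopsis nor 5.4.1 says the stated step stops applying below DL 1.

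**Conclusion.** Both points hold as errors in operative dosing text that should be corrected. The increase on recovery has no counterpart in Section 5.4. The stated ruxolitinib step is right for the three increases from DL 1 upward and wrong for all three below it: two skip a level and one leaves the table.

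This rests on Table 2 as printed, on 5 mg BID meaning 5 mg added to each daily dose, and on Section 5.4 being the governing text. It is not a finding that compliant dosing is impossible. Nor should a reader infer bias in the efficacy comparison: the documents do not give the number of subjects who would be re-escalated from below DL 1, and no effect on the primary analysis is shown.

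**What to change.** 1. In 5.2.1.1 and 5.2.2.1, say that a held dose may be restarted per Table 1 and that any increase must meet Section 5.4.1. Allow no increase while a Table 1 reduction limit is in force (hematocrit < 35%, ANC < 1.5 × 10^9/L, platelets < 150 × 10^9/L). Name hematocrit explicitly, because 5.4.1 tests hemoglobin instead.
2. In the synopsis and 5.4.1, correct the ANC criterion to 1.5 × 10^9/L.
3. In the synopsis, 5.4.1 and 5.4.4, state that each increase is at most one Table 2 level: +5 mg/day ruxolitinib and +0.5 mg/day anagrelide below DL 1; 5 mg BID ruxolitinib with the two-week anagrelide steps from DL 1 upward. In 5.4.4, make clear that this applies to each drug given alone. Keep it subject to the existing bar on returning to a dose not previously tolerated.

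The cost is protocol wording and a site communication, with no new visits, samples or subjects. Returning from DL -2 to DL 1 would take two increases at least a week apart instead of one.
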